An orally available, antiinflammatory drug, with a good safety and tolerability profile is still an unmet need in MS treatment. Frankincense extracts have already shown this profile in a couple of clinical trials of different autoimmune diseases. The triple inhibition of cathepsin G, mPEGS-1 and 5-LO offers a novel pharmacological approach in the treatment of multiple sclerosis that has not been studied so far.

Here we propose a study design to test the safety, tolerability, efficacy and mechanism/s of action of BA in a Phase IIa proof-of-concept baseline-to-treatment study in relapsing-remitting MS or CIS patients with the standardized frankincense extract BOSWELAN. Dose finding, assessment of tolerability and efficacy on contrast-enhancing MRI lesions will be accompanied by mechanistic studies that will address by ex vivo and in vitro experiments if treatment with the frankincense extract only affects the above enzymes or has further pharmacodynamic effects.

Study Objective: To determine the safety and tolerability of BOSWELAN in subjects with multiple sclerosis or clinically isolated syndrome and to describe the effect of Boswellic acids on the disease activity as assessed by monthly MRI measures.

Number of Subjects:

75 subjects will be enrolled to obtain at least 30 subjects completing 8 months of treatment at a t.i.d. (Ter In Die (*Latin: Three Times A Day*)) dose of between 400-1600 mg. It is estimated that 75 patients will undergo baseline MRI assessment in order to identify 30 patients meeting the MRI entry criteria.

Study Population: Clinically isolated syndrome (CIS) or relapsing-remitting Clinically definite MS (CDMS) with an age between 18 - 65 years
Baseline number enhancing lesions 0.5 or greater per month

Safety Parameters and Stopping

rules: Stage 1 – 4 (dose finding, stabilization, a continued treatment phase and a follow-up):

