The individual well tolerated dose from Stage 1 will be used for each patient in a subsequent 4-week stabilization phase during which the dose will be observed for continuous safety and toleration. Afterwards this individual maximal well tolerated dose will be used in Stage 3 of the study for further 6 months. Patients not tolerating the minimum dose of 800mg t.i.d. will be excluded from the study.

Stage 3

In Stage 3 of the study, patients will be treated with their individual well tolerated dose of BOSWELAN as assessed in Stage 2 subsequently for six months. The minimum dose for patients to be considered evaluable in the primary statistical analysis will be 800mg t.i.d..

The primary outcome will assess the change in mean Gd-enhancing lesion number from the baseline to that observed over months 5, 6, 7 and 8 since a delay in treatment effect is expected. In addition to MRI evaluation, patients will have monthly neurological evaluations and immunological assessment.

Stage 4

After completing Stage 3 patients are offered to continue their BOSWELAN dose for 4 months or to stop drug intake after month 8. In any case patients are seen for clinical and MRI-follow-up at month 12 at the study center.

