2.5.2 Dose justification

In conclusion from the abovementioned studies we deduce as minimum effective dose 800mg t.i.d., which is sufficient to induce plasma levels of AKBA *in vivo* that have previously been shown to inhibit Cathepsin G *in vitro*. The other two enzymes that are relevant to be inhibited by boswellic acids in the context of MS, namely 5-LO and mPGE1 require higher doses between 1-10µM of AKBA for inhibition, and consequently higher doses of BA extracts are probably needed to achieve these effects. 4800 mg/d (1600 mg t.i.d.) is the highest dose that we are planning to administer in this study because frankincense extracts have been reported to be safe and well tolerated up to this dose (45,46,54,55) and due to their higher efficacy that has been shown in studies of cerebral malignancies.

The minimal no observable adverse effect level (NOAEL) as documented in the toxicology studies translates to the following human equivalent doses (HEDs):

Table 1: Translation of minimal NOAEL doses from rat / dog to man

Species	NOAEL/LTD mg/kg	mg/kg	mg/m2
Rat	300	300	1770

	600	600	3540
	900 (LTD)	900	5310
Man/Rat		6.8	253
		13.7	506
		20.5	759
Dog	100	100	2000
	300 (LTD)	300	6000
Man/Dog		27	1000
		81	3000

Source: Guidance for Industry. Estimating the Maximum safe Starting Dose in Initial Clinical Trials for Therapeutics in Healthy Adult Volunteers. US CDER, July 2005, Pharmacology and Toxicology

The doses used with *Boswellia serrata* extract formulations in man to date range from approximately 1200 mg to 4800 mg per day divided over 3 daily doses. Clinical experience indicates that, dependent on the indication, optimal daily doses range between 3600 mg and 4800 mg/day in the acute phase or during initiation of treatment (below also referred to as higher, previously applied dose range) and between 1200 mg and 2400 mg/day (below also referred to as intermediate dose range) during maintenance therapy.

Therefore, the highest applied daily human dose (3600 mg – 4800 mg, approx. 70 kg b.w.) is between 51,4 - 68,5 mg/kg and 17,1 - 34,3 mg/kg for the maintenance doses based on the conversion standards as provided by the FDAs “Guidance for Industry. Estimating the Maximum safe Starting Dose in Initial Clinical Trials for Therapeutics in Healthy Adult Volunteers”, US CDER, July 2005, Pharmacology and Toxicology.

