7.1 Treatment Schedule

BOSWELAN is provided as capsules containing 400 mg of the frankincense extract.

Patients must be advised to swallow the capsules with a full glass of liquid before or during a meal.

Definition of “not tolerated”: Persisting moderate adverse events at the next dosing time point or whenever the investigator feels that the dose has to be (temporarily) reduced or dosing be omitted.

Definition of “well tolerated”: No or mild adverse events which have resolved before the next dose. Since the definition of the highest well tolerated dose will in most cases be done retrospectively after first moderate or severe adverse events occurred, establishing the highest well tolerated dose will include at least one dose above this dose level. Whenever the definition of “not tolerated” is fulfilled, the dose will be reduced until the “well tolerated” dose is established.

“Dose” is defined as any daily dosing regimen which also allows for different number of capsules at the 3 dosing time points per day.

BOSWELAN will be titrated up to the maximum well tolerated dose or to a maximum of 1600 mg t.i.d (whatever occurs first). The dose titration period will occur over 28 days (stage 1). After determining the maximum well-tolerated dose, each patient will be continued on this dose for another 28 days for dose tolerability and stabilization (stage 2), followed by additional 6 months of treatment (stage 3). Subsequent adjustments to the dose will be made as necessary. Patients are offered to continue drug intake after completing stage 3 during the follow-up stage.

The titration rules for the dose finding period stage 1 of the study are as follows:

A dose increase will be performed only if the previous dose was sufficiently tolerated, i.e. no adverse event or only mild adverse event(s), which has resolved at the next dosing time point.

If an increase in dose is not tolerated, the dose will be temporarily reduced. There should be no more than 3 temporary dose reductions during the dose escalation phase, i.e. after a third dose reduction the dose will be fixed at that or a lower well tolerated dose level.

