7.2 Dose Titration Scheme

The dose unit for the following titration scheme has been set as 400 mg/capsule. Dosing is at morning, midday and evening with at least 6 hours between doses.

BOSWELAN will be titrated up to the highest well tolerated dose or to a maximum of 3 x 1600mg during Stage 1.

The dose titration period will be up to 28 days. The dose reached at that time point should be the maximum dose that is well tolerated.

Titration scheme: The dose unit has been set as 400 mg/capsule.

Days	Dosing schedule	Special measures
0	1-0-0	
1:	1-1-1	phone contact on Day 1 before morning dose
2-3	1-1-2	
4-6:	2-1-2	phone contact on Day 4 before morning dose
7-9:	2-2-2	
10-12:	2-2-3	
13-15:	3-2-3	phone contact on day 13 before morning dose
16-18:	3-3-3	
19-21:	3-3-4	
22-24:	4-3-4	
25-28:	4-4-4	

It is expected that adjustments to this schedule will be needed in the event that side effects occur or if dose reductions are necessary. However, patients should remain on each new dose for a minimum of 3 days before the next increase.

Any re-increase of dose after a dose reduction due to an adverse event requires consultation by phone with either the treating physician or the study nurse. In case of a serious adverse event (SAE), dosing will be stopped until the SAE has resolved. Dosing will then resume at a reduced dose level. If dosing is stopped for greater than 2 weeks, the study medication will be stopped in that patient and the patient will be withdrawn prematurely from the study.

Any intolerance of moderate or severe degree must be reported by the patient to either to the treating physician or a study nurse by phone.

The first dose will be administered in the respective Clinical Center. Each patient will contact the study nurse on days 1 (before morning dose), 4 (before morning dose), and on day 13 (before morning dose). Patients will be seen at the center

on days 0 and day 28 and the morning dose will be administered at the center on these days (in case of participating in the pharmacokinetic sub-study).

Treatment of adverse events is at the investigator's discretion.

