13.1 Sample Size Considerations

Based on analyses of a natural history cohort studied with monthly MRIs for a minimum of one year, a baseline to treatment designed trial incorporating 4 baseline MRIs and 4 treatment MRIs will require 12 patients to detect a 60% reduction in Gd-enhancing lesions with an alpha of 0.05 (one-sided). Regarding BA we expect an efficacy of 40% reduction of inflammatory lesions (Gd-enhancing) and estimate that 30 patients will be required to detect a 40% reduction with a power of 0.8 and an alpha of 0.05 (one-sided). Sample size estimation is based on published statistical simulations (64).

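### Section 2.3 removes patients who do not tolerate 800 mg t.i.d., yet the Summary counts 8-month completers from 400 mg t.i.d. towards the target of 30

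*Protocol*

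**What the plan says.** **Who stays.** Section 2.3, Stage 2: "Patients not tolerating the minimum dose of 800mg t.i.d. will be excluded from the study". The Summary's own Stage 2 text instead moves a patient who cannot tolerate the Stage 1 dose to the highest dose that patient does tolerate, and names no minimum. Section 7.1 likewise reduces the dose until it is well tolerated, fixes it after a third reduction, and sets no floor. It defines a dose as "any daily dosing regimen which also allows for different number of capsules at the 3 dosing time points per day". The list of withdrawal reasons in Section 7.3.1 does not include failure to tolerate 800 mg t.i.d.

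**Who counts towards 30.** Summary, Number of Subjects: "75 subjects will be enrolled to obtain at least 30 subjects completing 8 months of treatment at a t.i.d". The range that follows is a "dose of between 400-1600 mg".

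**Who is analysed.** Section 2.3, Stage 3: "The minimum dose for patients to be considered evaluable in the primary statistical analysis will be 800mg t.i.d". The Summary (Statistical Plan), Section 3.2 and Section 14 apply the same threshold to the primary comparison of the baseline MRIs with months 5 to 8. Section 2.5.2 gives the rationale: "we deduce as minimum effective dose 800mg t.i.d".

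**What 30 was sized for.** Section 13.1, for a design with 4 baseline and 4 treatment MRIs: "30 patients will be required to detect a 40% reduction with a power of 0.8 and an alpha of 0.05 (one-sided"). No dose is named there or in the Summary's sample-size paragraph.

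**The concern.** If the Stage 2 rule is applied, a patient whose tolerated dose is below 800 mg t.i.d. leaves at about month 2 and cannot be an 8-month completer. If the Summary and Section 7.1 are applied, the same patient continues on drug to month 8 and counts towards the 30.

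Two things depend on this: how long such patients are treated, and when the target is met. A completer below 800 mg t.i.d. takes one of the 30 places and prompts no replacement, yet is left out of the primary comparison. That comparison could then hold fewer than 30 patients although the target as written has been reached.

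**Working it through.** **1. Can a patient settle below 800 mg t.i.d.?** Section 7.2: "The dose unit for the following titration scheme has been set as 400 mg/capsule". After the single first-day capsule, the steps are:

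| Step | Capsules | mg/day |
|---|---|---|
| 1-1-1 | 3 | 3 × 400 = 1200 |
| 1-1-2 | 4 | 4 × 400 = 1600 |
| 2-1-2 | 5 | 5 × 400 = 2000 |
| 2-2-2 (800 mg t.i.d.) | 6 | 6 × 400 = 2400 |

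Three steps fall inside the Summary's range and below the Section 2.3 minimum. Section 7.1 allows a patient to be fixed at any of them.

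**2. Does the 30 belong to the dose-restricted comparison?** Section 13.1 assumes 4 baseline and 4 treatment MRIs. Section 3.2 describes the primary efficacy comparison in those terms (months 5 to 8, at least 800 mg t.i.d.). The secondary analysis uses all treatment months, which Section 10.1 scans seven times (months 1, 2, 3, 5, 6, 7, 8). The 4-versus-4 design therefore matches the restricted comparison. This is an inference, because no dose is stated.

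**3. The plan's own figure.** The 30 cannot be rebuilt: the protocol gives no SD, lesion rate or correlation and relies on published simulations. With the paired normal formula n = ((1.645 + 0.842) × SD/δ)²:
- 30 patients at a 40% reduction imply δ/SD = 2.487/√30 = 0.454, so SD is about 0.88 of baseline.
- 12 patients at a 60% reduction (Section 13.1; power 0.8 assumed, as none is stated for that figure) imply SD of about 0.84. Scaling to 40% gives 27 patients (26 with a t-based calculation, 39 on a log-ratio scale).

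These values bracket 30 but neither confirm nor refute it. The dose conflict does not depend on them.

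**4. Power if completers below 800 mg t.i.d. are counted.** The protocol gives no rate for this. Assumption: 1, 2 or 3 of the 30. Calibrating to the stated 0.80 at n = 30, power(n) = Φ(0.454 × √n − 1.645):

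| Below 800 mg t.i.d. | Evaluable n | Power, normal | Power, paired t |
|---|---|---|---|
| 0 | 30 | 0.800 | 0.800 |
| 1 | 29 | 0.788 | 0.787 |
| 2 | 28 | 0.776 | 0.774 |
| 3 | 27 | 0.762 | 0.760 |

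This approximates a Wilcoxon signed-rank analysis and does not re-run the cited simulations.

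**5. Scans lost if the exclusion is enforced.** A patient leaving at about month 2 has on-treatment scans at months 1 and 2 only. The scans at months 3, 5, 6, 7 and 8 are lost, 5 of 7. For 1, 2 or 3 patients that is 5, 10 or 15 scans. Any scan in the 2-month follow-up under Section 7.3.1 is off drug. The primary comparison is not affected, since these patients would not be in it. The loss falls on the analyses over all treatment months, including the intention-to-treat analysis.

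**The case against.** The best defence is that the passages describe different moments. The exclusion stands in the Stage 2 paragraph, and Section 7.1 allows later dose adjustments. A patient who tolerates 800 mg t.i.d. in Stage 2 and is reduced in Stage 3 can finish below it without breaching the rule. The Stage 3 evaluability sentence makes most sense if such patients exist. That much stands. It does not cover a patient whose tolerated dose is already below 800 mg t.i.d. at the end of titration or stabilization.

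It can also be said that the Summary's range is only a target, and that Section 7.3.1 lets the investigator withdraw a patient for medical or other reasons. But that clause permits withdrawal where Section 2.3 requires it.

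A reader might infer that 400 mg is simply a slip for 800 mg. The documents do not settle this. Section 2.2 says active concentrations are reached at 3 × 400 mg/day, the Summary sets no floor in Stage 2, and a wide range suits a primary objective of safety and tolerability. The dose-restricted passages define an analysis set and do not say who remains in the study.

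A reader might also infer a serious loss of power. Nothing supports that. Section 2.5.1 reports adverse events in at most 5% of treated patients and no serious events in 38 patients on 800 mg t.i.d. for a year. These are not rates of dose failure, but they suggest few such patients.

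**Conclusion.** The point holds as a minor internal inconsistency. The text conflicts on whether a patient who cannot tolerate 800 mg t.i.d. by the end of Stage 2 is withdrawn, or continues and counts towards the 30.

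The textual conflict is certain. The link between the 30 and the 800 mg t.i.d. comparison is a sound inference from the MRI design. The size is an illustration only: a loss of about 1 to 4 percentage points of power, resting on an assumed 1 to 3 patients and a normal approximation.

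It would be wrong to conclude that the primary analysis set is undefined. The 800 mg t.i.d. threshold for it is consistent throughout, and the safety population in Section 13.3 is the same under either reading.

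**What to change.** 1. In the Summary, state the target as at least 30 subjects completing 8 months at 800-1600 mg t.i.d. and evaluable for the primary comparison.
2. Make the withdrawal rule consistent, with the sponsor confirming which was meant:
   - **Exclusion intended:** add failure to tolerate 800 mg t.i.d. by the end of Stage 2 to Section 7.3.1, and state that these patients' data stay in the safety and intention-to-treat analyses.
   - **Continuation intended:** in Section 2.3, Stage 2, replace exclusion from the study by *not evaluable in the primary efficacy analysis*.

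**Cost.** Either route takes two or three short text edits and changes neither the visit schedule nor the primary analysis. Continuation keeps a few patients for up to six more months on a dose below the stated minimum effective dose, while approved therapy is deferred (Section 16.2).

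Under both routes a patient below 800 mg t.i.d. must be replaced to reach 30. At the planned yield of 30 from 75 screened, that is 75/30 = 2.5 screened per replacement, or about 3, 5 or 8 more for 1, 2 or 3 patients. The wording alone does not secure 30 evaluable patients: the 75 is set to find 30 who meet the MRI entry criteria, with no stated allowance for dropout.

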2.4 Preclinical Studies

The pharmacology of the frankincense extracts has been examined in multiple studies *in vitro* and *in vivo*. With respect to its toxicology, frankincense extracts have been studied comprehensively for all relevant toxicity endpoints. The LD50s in mg/kg after oral application were found to be: >2000mg/kg for rats, mice, doses of 2000 mg/kg orally or intraperitoneal have not caused death in rats, mice and monkeys, high doses have reportedly not yielded significant effects on behavior or clinical, hematological, biochemical and pathological data (1, 45).

Single dose toxicity studies were performed in mice, rats and dogs by oral, i.m. and i.p. application. The acute toxicity was above 5000 mg/kg b.w. for the rat by oral administration (Laboratory of Pharmacology and Toxicology, Hamburg, Germany (LPT), Investigator's Brochure for BOSWELAN).

Subacute toxicity studies with an alcoholic extract of salai-guggal in rabbits over three months, and chronic toxicity studies in rats and monkeys over six months, have found no toxic effects of boswellic acids at high doses (45). A 26-week toxicity study in rats and a 9-month toxicity study in dogs were conducted at LPT according to the current ICH- and GLP-guidelines. In the 26-week chronic toxicity study in Sprague-Dawley rats, *Boswellia* extract was administered orally at dose levels of 300, 900 and 2700 mg/kg b.w./day. At 2700 mg/kg b.w./day substance-related mortality was noted. Hence, the dose level of the high-dosed male rats was reduced to 1800 mg/kg b.w./day from test week 15 onwards. None of the rats treated and also none of the surviving rats then treated with the low or intermediate dose showed any clinical signs of toxicity. The macroscopical inspection of the prematurely deceased high-dosed animals revealed a reduction in the size of the thymus. The relative liver weight of the intermediate and high-dosed rats was increased in a dose-related way (increase of 25 – 75% in comparison to controls).

In conclusion there were indications for a liver toxic influence of Boswellic acids at very high doses (46), at these high doses there was also a decreased urine volume and general body weight reduction observed.

In the 9-month chronic toxicity study in Beagle dogs, *Boswellia* extract was administered orally at dose levels of 300, 900 and 2700 mg/kg b.w./day. Due to the marked increased aP values in the intermediate and high dose groups, the dose levels were reduced to 100, 300 and 900 mg/kg b.w./day from test week 20 onwards. Moreover the increased levels of total bilirubin and total cholesterol are considered to be substance-related. The severity of the changes decreased after reduction of the dose levels from test week 20 onwards and all the above-mentioned changes had nearly disappeared at the end of the 4-week recovery period.

For assessing the genotoxic and carcinogenic potential studies were carried out by the Cytotest Cell Research and the GSF-Forschungszentrum für Umwelt und Gesundheit. Studies were performed for gene mutations in bacteria: (*Salmonella typhimurium* strains [CCR, 1987a]), gene mutations in eukaryotic systems (HPRT test in V79 cells [GSF, 1990]), chromosomal aberrations in human lymphocytes: in vitro [CCR, 1991] and chromosomal aberration test in bone marrow cells of the Chinese hamster [CCR, 1987b]. No mutagenic potential was observed for *Boswellia* extract [CCR, 1987a+b, 1991; GSF, 1990].

Carcinogenicity studies have not yet been considered necessary to be performed, as no reasons, e.g. chemical structure, previous demonstration of a carcinogenic potential in the product class that is considered relevant to man, or toxicological reasons including mutagenicity results, make such studies necessary. In addition, a cell transformation assay using Syrian hamster embryo (SHE) cells gave no indication for a carcinogenic potential [CCR, 1987c].

Since December 2014 estragole, a phenylpropene and natural organic genotoxic compound in various trees and plants like basil, anise, bay and also boswellia extracts has received new attention as shown by the recently drafted and still discussed public statement on the use of herbal medicinal products containing estragole (EMA/HMPC/137212/2005 Rev 1). Several studies in rodents have congruently established the genotoxic carcinogenicity of estragole in single substance studies (47-49).

Likewise metabolic activation and DNA binding occur also in human experimental systems in vitro. However it remains currently unclear if and to which extent these observations can be translated to humans as data from clinical studies are lacking and if the ingestion or application together with other compounds like in herbal extracts (50, 51) has comparable mutagenic effects. The EMA drafts and previous animal studies state that the mechanism of action of genotoxicity and carcinogenicity is dose-dependently conveyed by the production of reactive metabolites, primarily the sulfate conjugate of 1'-hydroxy estragole, which subsequently binds to DNA with possible genotoxic and carcinogenic potential (52).

Estragole is also used as flavoring agent in food products and has been approved by the US Food and Drug Administration (FDA), although the daily intake by consumers can only be estimated due to varying data on flavored and naturally estragole-containing food. Human data are missing but are estimated to lie between 0.5 to 5 mg estragole exposure daily.

The expert panel of the Flavor and Extract Manufacturers Association concluded in 2002 that dietary exposure to estragole from spice consumption does not pose a significant cancer risk to humans because several studies clearly established that profiles of metabolism, metabolic activation and covalent binding were dose dependent at high levels but diminished markedly at lower levels of exposure (49). The metabolic and genotoxic effects diminish markedly at low levels of exposure as described in the EMA guideline of 2005 (53).

Rodent studies show that genotoxic and carcinogenic events are probably minimal in the dose range of 1-10 mg/kg body weight in mice which is equivalent to 0,14 mg/kg – 1,43 mg/kg body weight in humans. This dose is approximately 100-1000 times higher than the anticipated human exposure to estragole by non-pharmaceutical ingestion. There are currently no regulatory established concentration limits for estragole in the area of medicinal products. The estragole doses in the study medication BOSWELAN have been shown to be below 0,14 mg/kg body weight. Yet these doses are significantly higher than the anticipated human exposure by ingestion, which will be pointed out in the patient information.

Embryotoxicity studies were conducted in rats and rabbits at LPT. Testing of the effect on fertility, reproductive capacity and peri- and postnatal development was not conducted since there was no indication that the reproductive organs had been affected by the test substance.

In rat embryotoxicity study the no-observed-effect level (NOEL) for dams was 300 mg Boswellia extract/kg b.w./day p.o.. In dams at 900 and 2700 mg/kg b.w./day a dose-related moderately reduced body weight and a reduction in food consumption were noted. There were no signs of embryotoxicity. The no-observed-effect level for the fetuses was above 2700 mg/kg b.w./day.

In conclusion, there were no signs of embryotoxicity including malformations, variations and/or retardations at any of the tested dose levels, even at materno-toxic doses [LPT, 2000f].

In the embryotoxicity study in rabbits, Boswellia extract was administered orally at dose levels of 50, 150, 450 and 1350 mg/kg b.w./day from the 6th to 20th day of pregnancy. The high dose of 1350 mg/kg b.w./day was included in this study as the dose of 450 mg/kg b.w. resulted in no clear maternal toxicity.

In conclusion, the test substance possessed no teratogenic properties. A marginal embryotoxicity was noted only at the materno-toxic dose of 1350 mg/kg b.w./day [LPT, 2000g].

